3.3 SVR as a measure of disease resolution

Although, the use of MgSO₄ is to prevent eclamptic seizures, the rarity of these events in the U.S. severely diminishes the feasibility of any research study with seizure mitigation as a primary outcome. **Therefore, a hemodynamic surrogate end point (SVR), based on the key mechanism of action of MgSO₄ as a vasodilator for eclampsia prevention, was selected.**

We are proposing to measure improvement in SVR using a novel, non-invasive, and well-validated hemodynamics monitoring system, as a criterion to discontinue MgSO₄, in the postpartum period. Although the exact etiology of eclampsia is still unknown, it is believed that cerebral vasospasm plays an essential role. It is hypothesized that in the setting of PE, and as blood pressure increases out of the normal range, cerebral resistance increases to limit cerebral perfusion. Ultimately, with increasing blood pressure and cerebral perfusion pressure, autoregulation is lost, which in the setting of endothelial dysfunction leads to vasogenic edema, overperfusion injury, and eclampsia. Magnesium is a calcium antagonist and can act on many calcium channels in the vascular smooth muscle. This leads to decrease in intracellular [Mg²⁺], inactivation of calmodulin-dependent myosin light chain kinase activity and reduced vascular tone, which subsequently leads to vascular (arterial) relaxation, and dilatation. Since vascular resistance is inversely related to the 4th power of blood vessel radius, effect of MgSO₄ on vasodilation has the most significant impact on peripheral and cerebral vascular resistance. This vasodilatory effect of MgSO₄, which we can detect peripherally, using Cheetah non-invasive cardiac monitoring, severs as a rationale for this study.

Clinical Protocol: Cheetah® OSU study

Therefore, we sought to demonstrate the utility of using improvement in SVR via non-invasive cardiac monitor as an indicator for resolution of PE, and individualize the duration of magnesium in the postpartum period for women with PE with severe features.

4 Hypothesis

We hypothesize that the use of the Cheetah® non-invasive cardiac monitor to individually determine the duration of magnesium sulfate postpartum (guided by timing of reduction in SVR) will result in shorter duration of MgSO4 infusion, compared with the traditional preset time point of 24hr postpartum, with no increase in maternal morbidity.

5 STUDY DESIGN

5.1 Type of Study

This is a single site pilot randomized, controlled, trial randomizing patients with PE with severe features to one of 2 groups:

- 24 hours of postpartum magnesium sulfate (current arbitrary standard of care)
- Using the Cheetah® device to aid in an individualized duration of magnesium sulfate based on reduction in SVR, up to a maximum of 24 hours postpartum.

A 30% reduction in SVR (maintained for 1 hour) from the time of delivery will be used as an indicator for resolution of PE and as the cutoff for discontinuation of magnesium sulfate. This SVR reduction is previously described in normal pregnancy within 1 hour postpartum² and similar reduction in SVR in pregnancies complicated by severe PE, from after delivery to 24-36hrs postpartum⁶.

In addition to subjects enrolled in the RCT, we propose an optional negative control cohort of 25 normotensive healthy women delivering > 37 weeks to compare hemodynamics.

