1 STUDY SYNOPSIS

Title	Use of Cheetah® non-invasive cardiac monitoring system to guide discontinuation of postpartum magnesium sulfate in women with severe preeclampsia: A pilot randomized control trial.
Objective	Demonstrate the utility of using improvement in SVR via non-invasive cardiac monitor as an indicator for resolution of preeclampsia, and individualize the duration of magnesium in the postpartum period for women with preeclampsia with severe features.
Study Population	Pregnant women greater than 18 years of age and 24 0/7 weeks' gestational age admitted to L&D for delivery with preeclampsia with severe features and plan to receive magnesium sulfate.
Study Design	This is a single site pilot randomized, controlled, trial randomizing patients with PE with severe features to one of 2 groups: 
• 24 hours of postpartum magnesium sulfate (current arbitrary standard of care)• Using the Cheetah® device to aid in an individualized duration of magnesium sulfate based on reduction in SVR, up to a maximum of 24 hours postpartum.
Eligibility	Subjects enrolled in the RCT must meet all of the inclusion criteria listed below: Inclusion Criteria 
• PE with severe features, diagnosed using the ACOG standard criteria⁴ requiring magnesium sulfate• Females older than 18 years of age• Singleton pregnancy• Gestational age greater than 24 0/7 weeks• The patient is physically and mentally able to understand the informed consent and is willing to participate in this study• Able to speak English or Spanish Subjects enrolled in the RCT must not have any of the exclusion criteria listed below: Exclusion Criteria 
• Multiple gestation• Prisoners• Patients with chronic renal insufficiency or epilepsy• Known cardiovascular disease• Patients with contraindications to magnesium sulfate use (e.g. myasthenia gravis)

Clinical Protocol: Cheetah® OSU study

	
• Patients with eclampsia or HELLP syndrome• Contraindications for magnesium sulfate 
(In addition to subjects enrolled in the RCT, we propose an optional negative control cohort of 25 normotensive healthy women delivering > 37 weeks to compare hemodynamics)

Site	The Ohio State University Wexner Medical Center

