3 BACKGROUND

3.1 Pregnancy hemodynamic changes

Pregnancy is a dynamic process associated with significant physiological changes in the cardiovascular system. These changes include an increase in cardiac output (CO), heart rate (HR), blood volume expansion, and a decrease in blood pressure (BP) and systemic vascular resistance (SVR) during pregnancy¹. On the other hand, labor is associated with significant hemodynamic changes, including increased CO and BP, and other parameters which are altered after administration of neuraxial anesthesia^{2,3}. Additionally, after the delivery of the placenta, there is a rapid return of CO and SVR to non-pregnant levels².

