Moreover, there is no consensus in the published trials regarding the optimal dose to use (both loading and maintenance), or the duration of therapy (especially in the postpartum period) ⁴. Multiple recent studies have questioned the utility of the use of magnesium sulfate for 24 hours postpartum and suggest no increased risk of eclampsia or maternal morbidity with use of shorter durations of use (such as 6 hours or 12 hours)¹²⁻¹⁴. However, most studies have no clear definition of a clinical parameter that defines the recovery phase from severe PE. One of several parameters that has been described as an indicator of clinical improvement from PE is the onset of diuresis¹⁵. This is believed to be a signal for reversal of increased SVR (vasoconstriction), and thus resolution of the disease. Historically, it was only possible to measure SVR with an invasive monitor such as a pulmonary artery catheter. The potential complications with these measurements outweighed the risk of benefit. Novel techniques including thoracic bioreactance, enable minimally invasive measurements of SVR and have been validated in the obstetric population.¹⁶

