5.3 Study Outcomes

Primary Outcome:

Duration of magnesium sulfate use in the postpartum period defined as the duration in hours between delivery and discontinuation of magnesium sulfate.

Secondary safety Outcome:

Composite of eclampsia, pulmonary edema, renal insufficiency/acute kidney injury, venous thromboembolism, peripartum cardiomyopathy, ICU admission, or maternal death.

Secondary Maternal clinical Outcomes

Maternal secondary outcomes

- Need for or up-titration of antihypertensive agents postpartum for severe hypertension
- Hospital readmission up to 4 weeks postpartum
- Changes in arterial blood pressure in the peripartum period
- Changes in cardiac output during the peripartum period
- Changes in heart rate in the peripartum period
- Need to restart magnesium sulfate
- Urine output, and the onset of diuresis defined as UOP >0.5ml/hour for 2 consecutive hours
- Preeclampsia symptoms resolution
- Correlation between magnesium levels and changes patient hemodynamics
- Anesthetic type
- Length of stay in Labor and delivery
- Total hospital length of stay
- Hospital cost
- Patient satisfaction

Clinical Protocol: Cheetah® OSU study

- Time to start regular diet and ambulation
- Maternal non-invasive cardiac parameters pre- and post-neuraxial anesthesia, pre- and post starting magnesium sulfate, with pushing or during cesarean delivery, and after the use of different anti-hypertensives (e.g. labetalol, nifedipine, hydralazine) for emergent therapy for severe hypertension
- Postpartum hemorrhage or blood transfusion
- Postpartum resources utilization including ER/triage visits, scheduled or non-scheduled clinic visits

Neonatal secondary outcomes

- Fetal or neonatal death
- Intubation, continuous positive airway pressure (CPAP) or high-flow nasal cannula (HFNC) for ventilation or cardiopulmonary resuscitation within first 72 hours
- Composite of either neonatal encephalopathy as defined by the NICHD Neonatal Research Network criteria, seizures, or intracranial hemorrhage (intraventricular hemorrhage, subgaleal hematoma, subdural hematoma, or subarachnoid hematoma)
- Hyperbilirubinemia requiring phototherapy or exchange transfusion
- Hypoglycemia (glucose < 35 mg/dl) requiring IV therapy
- NICU admission and length of stay in NICU

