7.2.1 Endpoint

This study's primary outcome is duration of magnesium sulfate use in the postpartum period, expressed in hours. The decision to discontinue magnesium in the Cheetah arm will be based on demonstration of 30% reduction in SVR (maintained for 1 hour) from the time of delivery.

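### No SVR reading is scheduled after an early magnesium stop, and the diuresis definition that could cross-check the stop is met by almost any urine flow

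*Combined protocol and SAP*

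**What the plan says.** The synopsis gives the objective as: "Demonstrate the utility of using improvement in SVR via non-invasive cardiac monitor as an indicator for resolution of preeclampsia", together with individualizing the duration of postpartum magnesium. Section 5.1 sets the rule: "A 30% reduction in SVR (maintained for 1 hour) from the time of delivery will be used as an indicator for resolution of PE", and the same sentence makes it the cutoff for stopping. Section 7.2.1 repeats the rule, with no condition on other drugs or on neuraxial block.

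The protocol itself names influences on SVR other than recovery:

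- Section 3.3, on magnesium: "This vasodilatory effect of MgSO₄, which we can detect peripherally".
- Section 3.1, on labor hemodynamics: "other parameters which are altered after administration of neuraxial anesthesia".
- Section 5.3 lists cardiac parameters around neuraxial anesthesia, around the start of magnesium, and "after the use of different anti-hypertensives (e.g. labetalol, nifedipine, hydralazine) for emergent therapy for severe hypertension".

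Section 5.3 also lists a magnesium-hemodynamics correlation, peripartum blood pressure, cardiac output and heart rate, symptom resolution, magnesium restart, and onset of diuresis (urine output above 0.5 ml per hour in two successive hours). Section 3.2 explains why diuresis matters: "This is believed to be a signal for reversal of increased SVR (vasoconstriction), and thus resolution of the disease".

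Section 5.4 plans collection of cardiac parameters, anesthesia and antihypertensive use, serial magnesium levels and hourly urine output. It says when the device goes on in the Cheetah arm. It does not say when it comes off, or whether the 24-hour arm wears it. Section 7.2.4 makes everything except the primary analysis exploratory.

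**The concern.** The trigger is read on treatment. To support the resolution half of the objective, one would want to know whether the fall held once magnesium was off, and whether independent signs of recovery were present at the stop. The plan schedules no reading for the first question. For the second, it collects the ingredients but names no summary that places them relative to the stop, and the diuresis definition cannot separate recovering women from others.

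The reference for the 30% figure does not fill the gap. Section 5.1 cites it for normal pregnancy within an hour of delivery. For severe preeclampsia it cites only a "similar reduction in SVR in pregnancies complicated by severe PE, from after delivery to 24-36hrs postpartum". Early stops fall before 24 h, where the plan offers no severe-preeclampsia reference value.

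At stake is how far the pilot can support SVR as a resolution indicator before a larger trial relies on it. SVR readings not taken in the hours after a stop cannot be recovered later.

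**Working it through.** **1. Diuresis threshold (Section 5.3).** The minimum qualifying volume is 0.5 ml/h × 2 h = 1 ml. A full day at that rate is 0.5 × 24 = 12 ml. Almost any urine flow passes, so onset would be recorded at about the first two hours of measurement in nearly every woman, whatever her recovery.

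**2. What the SVR ratio contains.** Let S0 and S1 be the underlying SVR at delivery and at the trigger, and d0 and d1 the proportional lowering by drugs or block at each time (assumed multiplicative). Then

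observed ratio = (S1/S0) × (1 − d1)/(1 − d0).

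- Steady magnesium effect, d0 = d1 = m: the factor is 1, and an observed 0.70 is an underlying 0.70 for any m.
- Added vasodilation after delivery (an acute antihypertensive dose, a rising magnesium level), d1 > d0: the trigger is easier to reach.
- A block present at delivery that lowered SVR and has worn off, d1 < d0: the trigger is harder to reach.

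The documents give no value for d0 or d1, so neither the net sign nor the size can be stated.

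**3. Are the planned data tied to the stop?** Section 5.3 attaches its cardiac parameters to the anesthetic, the start of magnesium, or an emergent antihypertensive dose. Its magnesium correlation has no time reference. Section 7.2.4 names race, gestational weeks and BMI as covariates, plus unspecified significant variables. None of these refers to the qualifying hour or the stop.

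**4. Size of the added readings.** Inputs from Section 7.2.5: 21 required per arm; 60 enrolled, so 30 per arm if allocation is equal; average reduction 4 h. The 21 cannot be reproduced from stated inputs because no SD is given. An SD of 4 h gives 2 × (1.960 + 1.282)² × 4²/4² = 21.0. The figure is used here only as a head count. Assumed: 40% to 80% of Cheetah-arm women stop early, and the rest, like the 24-hour arm, run to 24 h.

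- Early stoppers: 0.4 × 21 = 8.4, about 8; 0.8 × 30 = 24.
- Hours off magnesium before 24 h, per early stopper: 4/0.8 = 5 h; 4/0.4 = 10 h.
- Readings each, at one per 2 h: 5/2 = 2.5 to 10/2 = 5, so 2 to 5.
- Readings in total: 21 × 4/2 = 42; 30 × 4/2 = 60.

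**5. What they could show.** Half-width of the 95% CI for mean SVR change after the stop = t(0.975, n−1) × SD/√n, with an assumed SD of 10 to 20 percentage points.

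- n = 8, SD 20: 2.365 × 20/2.828 = 16.7 points.
- n = 24, SD 10: 2.069 × 10/4.899 = 4.2 points.

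For the proportion of early stops with a recent antihypertensive dose, taking 25% as an example, the exact 95% CI is 3.2% to 65.1% for 2/8 and 9.8% to 46.7% for 6/24. Both results can only be descriptive.

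**The case against.** The best case for the plan is that this is a small pilot whose formal hypothesis (Section 4) is shorter magnesium without more morbidity. It says indicator, not proof, and Section 3.3 already calls SVR improvement a criterion for stopping. Stop time is the primary outcome, and urine output is hourly, so most of the timing could be derived afterwards, including diuresis under a corrected threshold. Cardiac-parameter collection in Section 5.4 has no stated end, so readings after the stop may well occur. Restart and the safety composite capture clinical failure. Added readings burden one arm only.

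Most of this stands. It keeps the priority low, and relabelling the criterion is unnecessary. It does not supply a schedule for SVR after the stop, and clinical failure is a different question from persistence of the fall. The diuresis entry may be a dropped unit, but as printed it is the definition the trial would apply.

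A reader might go further and infer the following, which the documents do not support:

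- *The trigger merely measures magnesium.* A steady effect cancels (step 2), and the direction of changing effects is not known.
- *Drug and block effects are ignored.* Section 5.3 lists them; only the link to the stop is missing.
- *The device comes off at the stop.* Nothing says so.
- *There is no SVR comparator at all.* An optional cohort of 25 normotensive women is proposed. If the 24-hour arm is unmonitored, what is lacking is a concurrent severe-preeclampsia comparator.

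**Conclusion.** The point holds in limited form. The diuresis definition is wrong as printed: 1 ml over two hours satisfies it. No SVR reading after the stop is scheduled, and no planned summary ties drug, block, symptom or diuresis timing to the stop. The pilot as written would show when SVR fell by 30% on treatment, but would not reliably show whether the fall persisted off magnesium.

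These conclusions rest on the text and need no assumed figure. Only the workload and precision in steps 4 and 5 depend on assumptions (share stopping early, SD, equal allocation). The effect is confined to how much weight the resolution reading can bear. Apart from the diuresis definition, which should be corrected, this is an improvement to consider.

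**What to change.** (a) Section 5.3: correct the diuresis threshold and its unit. Restoring a missing unit may not be enough; the value must separate diuresis from ordinary urine flow, which is a clinical choice. The hourly data are already planned, so the cost is a wording change.

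(b) Section 5.4: specify non-invasive SVR spot readings, for example every 2 h, to 24 h postpartum in Cheetah-arm women who stop early. Report the change from the trigger value with a 95% CI, as descriptive. By step 2, loss of magnesium's vasodilatory effect alone would raise SVR, so a rise does not by itself mean disease has returned. State in advance whether a rise prompts any action. Persistence would support resolution without establishing it, since time since delivery and continuing antihypertensives could also explain it.

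(c) Section 7.2: for early stops, tabulate any antihypertensive dose in a fixed window (for example 2 h) before or during the qualifying hour, block status at delivery and at trigger, and the timing of symptom resolution and diuresis relative to the stop. This uses mostly planned data; block status at trigger may need one CRF field.

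Also state whether the 24-hour arm is monitored.

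The cost is about 2 to 5 readings per early stopper, in women already fitted with the device. The burden falls in one arm and may affect ambulation, satisfaction or magnesium restarts, all secondary outcomes. The stopping rule, primary comparison and sample size stay as they are.

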3.2 Preeclampsia

Preeclampsia (PE) is a multisystem disorder affecting up to 8% of pregnancies and is diagnosed using standard clinical and biochemical criteria (Box 1)⁴. PE with severe features is diagnosed with either systolic blood pressure of 160mm Hg or more, or diastolic blood pressure of 110mm Hg or more on two occasions at least 4 hours apart (unless antihypertensive therapy is initiated before this time) and/or the presence of end organ injury such as thrombocytopenia, liver or renal injury, pulmonary edema, persistent symptoms (as defined in box 1) or eclampsia.

Globally, PE is a leading cause of morbidity and mortality for pregnant women. Pregnant women who develop PE are at risk of eclampsia, a serious complication defined as new onset seizures and/or unexplained coma in the setting of PE, stroke, placental abruption, coagulopathy, pulmonary edema, acute kidney injury, liver hematoma, intracranial bleeding, cardiopulmonary arrest, and death. Moreover, PE increases risk of future cardiovascular disease and represents a significant economic burden on healthcare systems⁵. Published literature has identified striking differences in the maternal hemodynamic profiles between normotensive pregnancies and those complicated by PE. **PE is associated with a significantly higher BP and SVR with lower HR, stroke volume, and CO⁶.**

Women with PE also have higher levels of placental-derived anti-angiogenic proteins and significantly lower levels of pro-angiogenic proteins, when compared with healthy pregnant women⁷. The increased SVR noted in pregnancies complicated by PE have been associated with abnormal plasma levels of angiogenic proteins^{7,8}.

The cure for PE has remained the same for several decades: delivery of the fetus and placenta. Immediately after birth, there is resolution of many of the clinical symptoms of PE, including a decrease or normalization in BP, improvement in urine output, and improvement of symptoms of end organ damage, along with reduction in stroke volume, CO, mean arterial pressure (MAP), and SVR⁶.

In the U.S., parenteral magnesium sulfate (MgSO₄) is routinely given to pregnant women for the prevention of eclampsia in patients with PE, especially those with severe features, as multiple

Box 1: Criteria for Diagnosis of PE
Systolic blood pressure of 140mm Hg or more, or diastolic blood pressure of 90mm Hg or more on two occasions at least 4 hours apart (unless antihypertensive therapy is initiated before this time)

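### The device-arm rule for stopping magnesium before 24 hours gives an SVR cutoff but no clinical condition for holding the stop

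*Combined protocol and SAP*

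**What the plan says.** Section 5.1 sets the device-arm rule: "A 30% reduction in SVR (maintained for 1 hour) from the time of delivery will be used as an indicator for resolution of PE". The same sentence gives this event a second role, "as the cutoff for discontinuation of magnesium sulfate". Section 7.2.1 restates it: "The decision to discontinue magnesium in the Cheetah arm will be based on demonstration of 30% reduction in SVR (maintained for 1 hour", counted from delivery. The only other limit is the 24-hour maximum, which caps the infusion and does not govern an early stop.

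Two wordings are softer. Section 5.1 describes the device as used "to aid in an individualized duration of magnesium sulfate based on reduction in SVR", and section 3.3 presents SVR improvement as one criterion for stopping, without calling it the only one.

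Section 3.2 defines severe features by "systolic blood pressure of 160mm Hg or more, or diastolic blood pressure of 110mm Hg or more" (on two occasions, unless treated sooner) and/or "end organ injury such as thrombocytopenia, liver or renal injury, pulmonary edema, persistent symptoms", or eclampsia.

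In section 5.3, blood pressure change, symptom resolution and the need to restart magnesium are secondary outcomes, and pulmonary edema belongs to the safety composite. None of them is a condition for stopping. The primary outcome is hours from delivery to discontinuation.

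**The concern.** The rule that removes seizure prophylaxis early looks at one hemodynamic quantity. The clinical signs that brought the woman into the trial do not appear in it. If staff apply it as written, a woman can meet the SVR criterion while a severe feature is still active and have magnesium stopped, and the primary outcome then counts her as a shorter duration.

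An SVR fall need not mean that the disease has resolved. Section 5.1 itself notes that a fall of this size is described within an hour of birth in normal pregnancy. Section 3.1 mentions "other parameters which are altered after administration of neuraxial anesthesia", and section 3.3 describes magnesium's own vasodilation as an effect "which we can detect peripherally, using Cheetah non-invasive cardiac monitoring".

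There is also a reproducibility cost. If bedside staff do override the SVR signal on clinical grounds, the tested intervention includes decisions that the plan neither defines nor asks anyone to record.

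**Working it through.** **Text check.** I read every section that bears on stopping magnesium: the synopsis, 3.3, 4, 5.1, 5.3, 5.4 and 7.2.1. Each gives the SVR condition, the 24-hour cap, or an outcome. None makes an early stop depend on pressure, symptoms or pulmonary edema.

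**Can the criterion be met at severe-range pressure?** Assume SVR is proportional to MAP/CO (mean arterial pressure over cardiac output), ignoring central venous pressure, with MAP = diastolic + (systolic − diastolic)/3. A 30% fall in SVR then requires

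CO after / CO at delivery = (MAP after / MAP at delivery) / 0.70.

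The pressures are illustrative. The 160 and 110 limits come from section 3.2.

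| At delivery (MAP) | At the stop (MAP) | MAP ratio | CO ratio needed |
|---|---|---|---|
| any | unchanged | 1.000 | 1.43 |
| 180/120 (140) | 160/110 (126.7) | 0.905 | 1.29 |
| 180/120 (140) | 160/80 (106.7) | 0.762 | 1.09 |
| 170/110 (130) | 160/80 (106.7) | 0.821 | 1.17 |

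The 160/80 rows still count as severe because section 3.2 joins the two limits with an or.

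With CO unchanged from 180/120, MAP must reach 0.70 × 140 = 98. At systolic 160 that means a diastolic of (3 × 98 − 160)/2 = 67, a pulse pressure of 93. If CO falls, as section 3.2 describes after birth, MAP must go below 98. Severe-range pressure at the stop is then unlikely.

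Symptoms and pulmonary edema do not enter the formula, so it says nothing about them.

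**What a hold would cost in power.** Section 7.2.5 gives a 4-hour reduction, 5% alpha, 90% power and 21 per arm, but no SD, so the 21 cannot be reproduced directly. Section 7.2.2 makes tests two-sided. Solving the two-sample t-test for 21 per arm gives a standardized difference of 1.025, so the implied SD is 4/1.025 = 3.90 h.

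Retained sample: 60/2 = 30 per arm (1:1 assumed), and 30 × 0.85 = 25.5, taken as 25.

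Mean saving = 4 − (fraction delayed × hours lost). Power is from the noncentral t with 25 per arm and SD held at 3.90 h:

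| Share of device arm delayed by 4 h | Mean saving | Power |
|---|---|---|
| none | 4.0 h | 94% |
| 5% | 4 − 0.05 × 4 = 3.8 h | 92% |
| 10% | 4 − 0.10 × 4 = 3.6 h | 89% |
| 20% | 4 − 0.20 × 4 = 3.2 h | 81% |

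**The case against.** The strongest reply is that the rule is deliberate. The trial exists to test SVR as the marker of resolution, and a combined rule tests something else. Section 3.2 cites studies of 6- and 12-hour regimens that suggest no added eclampsia or morbidity. The control arm also stops at 24 hours without a stated clinical check. All of this is correct, and the first part stands as a real cost of the change. The cited studies support shorter durations in general, and the proposed hold sets no minimum duration. The 24-hour stop is what the protocol calls standard care, whereas the early stop is the departure that needs a safeguard.

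A second reply is that silence is not prohibition. Treating clinicians keep their judgement, as the softer wording in 5.1 and 3.3 implies. This also stands. A reader might infer that SVR alone must decide and that clinicians may not intervene, but the documents do not say so. The gap is that no condition is written down.

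Third, the physiological arguments are thin. Section 3.1 does not name SVR among the parameters that neuraxial anesthesia alters, and it gives no direction. Magnesium starts before delivery, so part of its effect is already in the baseline. Section 5.3 also plans to measure hemodynamics around both. A reader might infer that these effects produce false stops, but the documents do not show that. Nor is it right that SVR could never be compared with clinical status at the stop. Stop time, pressure and symptoms are all collected, and what is missing is a prespecified comparison.

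**Conclusion.** The omission is clear on the text: the plan gives one cutoff for stopping magnesium before 24 hours in the device arm and no clinical condition for holding that stop. A woman with persistent severe-range pressure or severe-feature symptoms could therefore be stopped under the rule as written. How often is unknown and probably uncommon. For pressure it needs cardiac output to rise, by about 9% to 43% in the 180/120 examples, under the proportionality assumption. For symptoms and pulmonary edema the documents give no basis for an estimate.

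A reader might go further and infer that the rule breaches the statement in section 5.8 that the device will not be used diagnostically without confirmation. The documents do not support that. The clause may concern only the diagnosis of preeclampsia, and nothing links it to stopping magnesium. The contents of the safety monitoring plan that is still to be developed are not given and are not judged here.

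The trial remains valid without the change. This is an inexpensive safety and clarity improvement, worth considering.

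**What to change.** In 5.1 and 7.2.1, state that before 24 hours magnesium stops when the SVR criterion is met **and**, in the same 1-hour window, pressure is below 160/110 and no persistent severe-feature symptom is present. Otherwise the infusion continues and the check is repeated at the routine magnesium checks, unless there is magnesium toxicity or another clinical reason to stop. Pulmonary edema goes to clinician review; it should trigger neither automatic continuation nor automatic stopping. The 24-hour cap is unchanged.

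Record two times: when the SVR criterion was met and when the infusion stopped. The SVR-only time can then still be described against clinical status. Define the primary outcome on the first discontinuation, and report any restart separately, as 5.3 already lists.

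The cost is protocol wording, one more recorded time and a documented symptom check. Section 3.2 already describes frequent pressure monitoring on magnesium, but no schedule for symptom checks is stated, so that part is new work. The tested rule becomes SVR plus a safety hold, and some stops come later. Under the illustration above, a 4-hour delay in 5% to 10% of the arm takes power from 94% to 92% or 89%. The SD there is back-solved and held fixed, although delays would change it.
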